4.3 Follow-up period

4.3.1 Discontinuation visit

A Discontinuation Visit will be performed at the time AZD9291 is permanently stopped. Refer to [Table 1](#) for full details.

4.3.2 28 Day follow-up

As a minimum, telephone contact should be made with the patient 28 days (+/- 7 days) following the discontinuation of AZD9291 to collect new AEs and follow up on any ongoing AEs and concomitant medications (including any subsequent cancer therapy). Refer to Section 6.3 for full details on AE recordings during follow-up.

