6.3 Recording of adverse events

6.3.1 Time period for collection of adverse events

Adverse Events will be collected from time of signature of informed consent throughout the treatment period and including the safety follow-up period. The follow-up period is defined as 28 days after study treatment is discontinued. SAEs occurring in the follow-up period should be reported to AstraZeneca in the usual manner (see Section [6.4](#)).

Following discontinuation of AZD9291, SAEs considered related to study procedures should continue to be collected as outlined in [Table 8](#).

After the final database lock, there may be some patients remaining on study treatment. For these patients who are continuing to receive AZD9291 AstraZeneca will collect information (during the treatment period and for 28 days after last dose) on SAEs, deaths (including those due to disease progression), discontinuation due to AEs/SAEs and drug accountability only.

Table 8 Summary of recording and follow-up of adverse events and deaths

	Consent to Treatment Period	Until 28-day Follow-up Visit (safety follow-up period)	Post 28-day Follow-up visit but prior to progression (if applicable)	Post 28-day Follow-up visit and post progression (survival follow-up period)
Collect all new AEs in CRF	Yes	Yes	No	No
Collect all ongoing AEs in CRF	Yes	Yes	Yes	Yes
Collect all study procedure-related SAEs in CRF	Yes	Yes	Yes	Yes
Death due to AE, or unknown cause¹	Yes	Yes	No	No

¹ for example, death not due to disease progression, refer to Section [6.3.10](#)

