6.3.10 Handling of deaths

All deaths that occur during the study, or within the follow-up period after the administration of the last dose of investigational product, should be reported as follows:

- Death, which is unequivocally due to disease progression, should be communicated to the study monitor at the next monitoring visit and should be documented in the CRF module, but should not be reported as a SAE during the study
- Where death is not clearly due to disease progression of the disease under study the AE causing the death should be reported to the study monitor as an SAE within 24 hours. The report should contain a comment regarding the co-involvement of progression of disease, if appropriate, and should assign a single primary cause of death together with any contributory causes
- Deaths with an unknown cause should always be reported as a SAE but every effort should be made to establish a cause of death. A post-mortem may be helpful in the assessment of the cause of death, and if performed a copy of the post-mortem results (with translation of important parts into English) should be reported in an expedited fashion to an AstraZeneca representative within the usual timeframes

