8.5 Calculation or derivation of safety variable(s)

Adverse events

Adverse Events (both in terms of MedDRA preferred terms and CTCAE grade) will be listed individually by patient.

Any AE occurring before treatment with AZD9291 will be included in the data listings but will not be included in the summary tables of AEs.

Any AE occurring within 28 days of discontinuation of investigational product (ie, the last dose of AZD9291) will be included in the AE summaries. Any events in this period that occur after a patient has received further therapy for cancer (following discontinuation of AZD9291) will be flagged in the data listings.

A separate data listing of AEs occurring more than 28 days after discontinuation of AZD9291 will be produced. These events will not be included in AE summaries

Other significant adverse events (OAEs)

During the evaluation of the AE data, an AstraZeneca medically qualified expert will review the list of AEs that were not reported as SAEs and AEs leading to discontinuation. Based on the expert's judgement, significant AEs of particular clinical importance may, after consultation with the Global Patient Safety Physician, be considered OAEs and reported as such in the CSR. A similar review of laboratory/vital signs/ECG data will be performed for identification of OAEs.

Examples of these could be marked haematological and other laboratory abnormalities, and certain events that lead to intervention (other than those already classified as serious), dose reduction or significant additional treatment.

Safety Assessments

For change from baseline summaries for vital signs, laboratory data, LVEF, ECGs and physical examination, the baseline value will be the latest result obtained prior to the start of investigational product.

The denominator used in laboratory summaries will only include evaluable patients, in other words those who had sufficient data to have the possibility of an abnormality.

For example:

- If a CTCAE criterion involves a change from baseline, evaluable patients would have both a pre-dose and at least 1 post-dose value recorded
- If a CTCAE criterion does not consider changes from baseline, to be evaluable the patient need only have 1 post dose-value recorded

The denominator in vital signs data should include only those patients with recorded data.

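### The 28-day safety follow-up call may be made on day 21, and Table 8 ends new-AE collection at that call, so up to a week of the 28-day period can go unasked about

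*Supplement*

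**What the plan says.** Three parts of the protocol measure the safety period in days. Section 6.3.1 states: "The follow-up period is defined as 28 days after study treatment is discontinued". It requires collection over that whole period: "Adverse Events will be collected from time of signature of informed consent throughout the treatment period and including the safety follow-up period". Section 8.5 uses the same limit for reporting: "Any AE occurring within 28 days of discontinuation of investigational product" enters the AE summaries, and later events go to a separate listing.

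Two parts tie the period to a contact instead. Section 4.3.2 and the Table 1 window row allow 7 days either side: "telephone contact should be made with the patient 28 days (+/- 7 days) following the discontinuation of AZD9291 to collect new AEs". The Table 8 column for this period is headed "Until 28-day Follow-up Visit (safety follow-up period)". The row "Collect all new AEs in CRF" reads Yes up to that visit and No in both columns after it. The row "Death due to AE, or unknown cause" has the same pattern, with a footnote pointing to Section 6.3.10.

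Section 6.3.10 applies to deaths during the study or within the follow-up period after the last dose. It adds: "Deaths with an unknown cause should always be reported as a SAE".

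Neither amendment changes these rules. Amendment 2 redirects Table 1 footnote r to Table 8, so more now depends on that table.

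**The concern.** One safety period has two end points: day 28 in the text, and the date of a contact in the table. They agree only when the contact falls on day 28 or later, and the window lets it fall up to a week earlier. A site that calls on day 21 is within the visit window and can read Table 8 as ending its duty to record new AEs that day.

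What is at stake is the completeness of post-treatment AE data, which would then depend on when the call happened to be made. Safety is a secondary objective of this single-arm study, so there is no control arm with the same gap to compare against. Objective response rate (ORR), sample size and overall survival are not affected.

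Deaths are a separate matter. Take a death on day 40 of unknown cause. Table 8 says it is not collected under the row for AE or unknown-cause deaths. Section 6.3.10 may say it must be reported as a serious adverse event (SAE), depending on what 'during the study' covers.

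**Working it through.** **Inputs.** Safety period 28 days (6.3.1, 8.5). Contact at day 28 with a window of 7 days either side (4.3.2, Table 1). New-AE collection ends at the contact (Table 8).

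**Reproducing the 28 days.**
- Earliest contact: 28 − 7 = day 21. Latest: 28 + 7 = day 35.
- Days not covered by a scheduled enquiry = max(0, 28 − contact day).
- Contact on days 28 to 35: 0 days uncovered, so the stated period is reproduced. Onsets after day 28 go to the separate listing in 8.5.
- Contact on day 27: 1 day, 1/28 = 4%.
- Contact on day 21: 7 days, 7/28 = 25%. Here only 21 days are covered.

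**Is there a later contact that would pick these events up?**
- Progression follow-up (4.3.3) takes AEs as set out in Table 8, which says No for new ones.
- Survival follow-up (4.3.4) lists no AE enquiry.
- Section 6.3.2 covers SAEs that the investigator learns of and considers possibly related to AZD9291, at any time. It schedules no enquiry.

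**Average loss, by assumption.** The documents do not say how calls are distributed. If they were uniform over days 21 to 35 (15 possible days):
- mean uncovered time = (7 + 6 + 5 + 4 + 3 + 2 + 1)/15 = 28/15 ≈ 1.9 days per patient;
- 7/15 = 47% of patients would be called before day 28, losing 28/7 = 4 days each on average.

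**Share of onsets at risk after a day-21 call, by assumption.** The documents give no onset pattern. Suppose onset after stopping decays with half-life h, and let F(t) = 1 − 2^(−t/h). The share of 28-day onsets falling after day 21 is [F(28) − F(21)]/F(28):

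| Onset pattern | Share after day 21 |
|---|---|
| Constant | 25% |
| h = 28 days | (0.500 − 0.405)/0.500 ≈ 19% |
| h = 14 days | (0.750 − 0.646)/0.750 ≈ 14% |
| h = 7 days | (0.9375 − 0.875)/0.9375 ≈ 7% |

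**Deaths: the passages side by side.**
- *Broad reading of 6.3.10.* Table 1 footnotes n, o and q describe the study as including survival follow-up, and Section 9.3 ends the study at the last subject's last visit. A day-40 death of unknown cause is then an SAE under 6.3.10 and a No under Table 8.
- *Narrow reading.* The same sentence of 6.3.10 adds deaths within the follow-up period after the last dose. If 'during the study' already reached into survival follow-up, that addition would be redundant. Read as on treatment plus 28 days, 6.3.10 agrees with Table 8 apart from the timing of the visit.
- The protocol does not say which reading is meant.

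**The case against.** The strongest reply is that the collection period is stated and is 28 days. Section 6.3.1 defines it, Table 8 repeats the same defined term in its column heading, and 4.3.2 calls the telephone call a minimum and refers to 6.3 for detail. A site that calls on day 21 therefore still owes new AEs to day 28. This stands as a statement of duty, and it rules out saying that such a site is instructed to collect nothing more. It does not remove the gap: Table 8 gives a different stopping point, and no scheduled contact asks about the remaining days.

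A reader might go further in four ways that the documents do not support:
- *That SAEs and deaths in days 22 to 28 escape reporting.* Section 6.3.1 requires SAEs in the follow-up period to be reported, 6.4 does so whether or not they are considered related, and 6.3.10 expressly covers deaths in that period.
- *That an AE which led to stopping, such as suspected interstitial lung disease, would be lost.* Such an event is already recorded. Table 8 keeps ongoing AEs at Yes throughout, and 6.3.2 continues their follow-up.
- *That 8.5 claims every patient was observed for 28 days.* It is a rule on which events enter the summaries and sets no observation-time denominator.
- *That about half of patients lose time.* The 47% comes only from the uniform assumption.

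On deaths, a flat contradiction between Table 8 and 6.3.10 might also be inferred. The Table 1 footnotes that favour the broad reading concern questionnaire timing, and the narrow reading is tenable. Survival follow-up still records the fact of death.

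**Conclusion.** The point holds as an internal inconsistency with a bounded effect. The text sets a 28-day period; the contact window and Table 8 together allow scheduled new-AE collection to end on day 21. The maximum loss is 7 of 28 days (25%) for a patient called at the earliest permitted time, and it is zero for anyone called on day 28 or later. The mean of about 1.9 days per patient rests on evenly spread calls, and the 7% to 25% share of onsets after a day-21 call rests on assumed onset patterns. How many events would be missed cannot be derived from the documents.

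The exposure is mainly in non-serious AEs. For serious events and deaths within 28 days the reporting duty is intact, and the weakness is only that nothing scheduled prompts their discovery after an early call.

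The passages on deaths after the visit are ambiguous, not plainly contradictory, and need reconciling. The change is worth making because it removes the gap at almost no cost.

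**What to change.** - In Section 4.3.2 and Table 1, set the follow-up contact at 28 days with a window of 0 to +7 days.
- In Table 8, word the columns as until, and after, 28 days from last dose, so that the table matches 6.3.1 and 8.5. Rewording Table 8 alone would align the rules but leave an early call with no later enquiry, so both changes are needed.
- Reconcile the Table 8 row on deaths due to an AE or of unknown cause with 6.3.10, stating whether 'during the study' includes survival follow-up. This review does not choose between the two readings.

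The cost is amendment wording and no added contact. A call that would have been made on day 21 moves by 7 to 14 days, to between day 28 and the existing day-35 limit. With no contact before day 28, the uncovered time is 0 days for every patient reached within the window.

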4.3.3 Progression follow-up

Patients who discontinue AZD9291 for reasons other than progression will continue RECIST 1.1 assessments every 6 weeks (relative to first dose of AZD9291) for objective progression. In addition to RECIST 1.1 assessments, the following assessments are also required during this follow-up period as detailed in the Study Plan (see [Table 1](#)):

- EORTC QLQ-C30 and EQ-5D-5L every 6 weeks and at the time of progression.
- EORTC QLQ LC13 and PRO-CTCAE every 3 weeks and at the time of progression.
- Plasma for ctDNA collected every 6 weeks up to and including progression (corresponding with the RECIST assessments – and continuing after treatment discontinuation if this is in absence of progression)
- Adverse event collection detailed in [Table 8](#)
- Anti-cancer therapy collected every 6 weeks.

4.3.4 Survival follow-up

Assessments for survival should be made every 6 weeks (relative to first dose) following objective disease progression or withdrawn from treatment. Survival information may be obtained via telephone contact with the patient, patient's family or by contact with the patient's current physician. In addition to the survival status, the following assessments are also required post progression as detailed in the study plan (see [Table 1](#)):

- EORTC QLQ-C30 and EQ-5D-5L every 6 weeks.
- EORTC QLQ LC13 and PRO-CTCAE every 3 weeks.
- Anti-cancer therapy collected every 6 weeks.
- Subsequent response/progression data every 6 weeks until the first confirmed disease progression on a subsequent treatment.

Survival data will be collected up to the time of the final OS analysis. Patients should be contacted in the week following the data cut-off for the final survival analyses to provide complete survival data.

The status of ongoing, withdrawn (from the study) and “lost to follow-up” patients at the time of an overall survival analysis should be obtained by the site personnel by checking the patients notes, hospital records, contacting the patients general practitioner and checking publicly available death registries. In the event that the patient has actively withdrawn consent to the processing of their personal data, the vital status of the patient can be obtained by site personnel from publicly available resources where it is possible to do so under applicable local laws.

5. STUDY ASSESSMENTS

The Rave Web Based Data Capture (WBDC) system will be used for data collection and query handling. The investigator will ensure that data are recorded on the electronic Case Report Forms as specified in the study protocol and in accordance with the instructions provided.

The investigator ensures the accuracy, completeness and timeliness of the data recorded and of the provision of answers to data queries according to the Clinical Study Agreement. The investigator will sign the completed electronic Case Report Forms. A copy of the completed electronic Case Report Forms will be archived at the study site.

5.1 Efficacy assessments

5.1.1 RECIST 1.1

All imaging assessments including unscheduled visit scans should be collected on an ongoing basis and sent to an AstraZeneca (AZ) appointed Clinical Research Organisation (CRO) to enable independent central analyses.

For both Independent Central Review (ICR) and investigator review RECIST 1.1 criteria will be used to assess each patient's tumour response to treatment and allow calculation of ORR, PFS, DCR, DoR, and assess tumour shrinkage. The RECIST 1.1 guidelines for measurable, non-measurable, target and non-target lesions and the objective tumour response criteria [CR (complete response), PR (partial response), SD (stable disease) or PD (progression of disease)] are presented in [Appendix D](#). For ORR, a visit response of CR or PR must be confirmed by a later scan conducted at least 4 weeks after the initial response is observed. See [Section 4](#) for considerations related to RECIST 1.1 assessments.

The methods used at baseline for assessment of tumour burden [CT or MRI scans of chest and abdomen (including liver and adrenal glands)] must be used at each subsequent follow-up assessment. Any other areas of disease involvement should be additionally investigated based on the signs and symptoms of individual patients. CT/MRI scan of the brain should be performed in patients with known or suspected brain metastases. The baseline assessment should be performed within 28 days of treatment start. Assessments to be performed every 6 weeks relative to first dose until objective disease progression. It is important to follow the assessment schedule as closely as possible. If scans are performed outside of the scheduled visit \pm 1 week window interval and the patient has not progressed, every attempt should be

made to perform the subsequent scans at their scheduled time points. Any other sites at which new disease is suspected should also be appropriately imaged.

If the investigator is in doubt as to whether progression has occurred, particularly with response to non-target lesions (NTLs) or the appearance of a new lesion, it is advisable to continue treatment until the next scheduled assessment or sooner if clinically indicated and reassess the patient's status. If repeat scans confirm progression, then the date of the initial scan should be declared as the date of progression.

To achieve "unequivocal progression" on the basis of non-target disease, there must be an overall substantial worsening in non-target disease such that, even in the presence of SD or PR in target disease, the overall tumour burden has increased sufficiently to merit discontinuation of therapy. A modest "increase" in size of one or more non-target lesions is usually not sufficient to qualify for unequivocal progression status.

Categorisation of objective tumour response assessment at each visit will be based on the RECIST 1.1 criteria of response: CR, PR, SD and PD. Target lesion (TL) progression will be calculated in comparison to when the tumour burden was at a minimum (i.e. smallest sum of diameters previously recorded on study). In the absence of progression, tumour response (CR, PR, SD) will be calculated in comparison to the baseline tumour measurements obtained before starting treatment.

5.1.2 RECIST 1.1 Independent Central Review assessment

The primary analysis for this study will be based on ORR using Independent Central Review (ICR) of patients with measurable disease at baseline as assessed by the ICR, according to RECIST 1.1. All scans from all patients (with both progressive and non-progressive disease by investigator assessment), used in the assessment of tumours using RECIST 1.1 will be conducted. All imaging assessments including unscheduled visit scans will be collected on an ongoing basis and sent to an AstraZeneca appointed CRO to enable central analysis. Results of this independent review will not be communicated to Investigators and the management of patients will be based solely upon the results of the RECIST 1.1 assessment conducted by the Investigator.

5.2 Safety assessments

5.2.1 Laboratory safety assessments

Blood and urine samples for determination of clinical chemistry, haematology and urinalysis will be taken pre-dose at the times indicated in the Study Plan ([Table 1](#)). If clinical chemistry, haematology and urinalysis screening assessments have been performed within 14 days prior to starting study treatment they do not have to be repeated on Visit 2 if the patient's condition has not changed (no new treatment during this period of time, no new complication or aggravation).

Additional safety samples may be collected if clinically indicated at the discretion of the Investigator. The date and results (values, units and reference ranges) will be recorded on the appropriate eCRF.

The clinical chemistry, haematology and urinalysis will be performed at a local laboratory at or near to the Investigator site. Sample tubes and sample sizes may vary depending on laboratory method used and routine practice at the site. The number of samples/blood volumes is therefore subject to site-specific change.

The following laboratory variables will be measured:

Table 2 Laboratory Safety Variables

Clinical chemistry	Haematology
Serum (S)/Plasma (P)-Albumin	Blood (B)-Haemoglobin
S/P-ALT	B-Leukocyte
S/P-AST	B-Haematocrit
S/P-Alkaline phosphatase	B-Red blood cell (RBC) count
S/P-Bilirubin, total	B-Absolute leukocyte differential count:
S/P-Calcium, total	Neutrophils
S/P-Creatinine	Lymphocytes
S/P-Glucose (fasting on PK days only) ¹	Monocytes
S/P-Lactate dehydrogenase (LDH) ²	Basophils
S/P-Magnesium	Eosinophils
S/P-Potassium	B-Platelet count
S/P-Sodium	B-Reticulocytes
S/P-Urea nitrogen or Blood urea nitrogen	Urinalysis
	U-Glucose
	U-Protein
	U-Blood

¹ Patients will be required to fast (water only) for at least 8 hours prior to the collection of a fasting glucose sample required on PK days. Random glucose sample will be collected on non-PK days.

² LDH is an additional variable collected at Visit 1 only.

Additionally, at the Screening Visit, a pregnancy test (blood or urine tests are acceptable based on the site's standard clinical practice) will be collected for women of childbearing potential only (See Section 3.1).

The Investigator should make an assessment of the available results with regard to clinically relevant abnormalities. The laboratory results should be signed and dated and retained at

centre as source data for laboratory variables. For information on how AEs based on laboratory tests should be recorded and reported, see Section 6.3.

NB. In case a subject shows an AST or ALT $\geq 3 \times \text{ULN}$ or total bilirubin $\geq 2 \times \text{ULN}$ please refer to [Appendix E](#) ‘Actions required in cases of combined increase of Aminotransferase and Total Bilirubin – Hy’s Law’, for further instructions.

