5.2.4 ECG

All patients will have 12-lead digital ECGs performed at the study visits indicated in [Table 1](#). Twelve-lead ECGs will be obtained after the patient has been resting semi-supine for at least 10 minutes prior to times indicated and should be recorded at 25 mm/sec. All ECGs should be recorded with the patient in the same physical position. For each time point three ECG recordings should be taken within an approximate 5 minute period. Digital ECG recordings will be collected, analyzed and stored by a central ECG vendor.

In addition to the ECG requirements outlined in [Table 1](#), the Screening Visit and PK sampling days will require three ECGs to be performed at the following time points shown in [Table 4](#).

Table 4 Digital ECG recording requirements

Time relative to dose	Screening (baseline)	Cycle 1 Day 1	Cycle 2 Day 1	Cycle 3 Day 1
Pre-dose (± 5 min)	X ¹	X	X	X
1 hour (± 5 min)	X	X		X
2 hours (± 10 min)	X	X		X
4 hours (± 10 min)	X	X		X
6 hours (± 10 min)	X	X		X
8 hours (± 10 min)	X	X		X
10 hours (± 10 min)	X			X
12 hours (± 1 hour)	X			X
24 hours (± 1 hour)	X			X (D2, pre-dose)

¹ Since there is no dosing at Screening, ECG recordings should start at a time that would be consistent with planned dosing times at Cycle 1 Day 1, Cycle 2 Day 1 and Cycle 3 Day 1 (for baseline purposes).

After ECGs have been recorded as digital ECG files, a print-out will be made and the investigator or designated physician will review each of the ECGs and may refer to a local cardiologist if appropriate. A paper copy should be filed in the patient's medical records. If an abnormal ECG finding at screening or baseline is considered to be clinically significant by the investigator, it should be reported as a concurrent medical history condition. If there is a clinically significant abnormal ECG findings during the treatment period, this should be recorded on the AE CRF, according to standard adverse events collection and reporting processes.

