2 **Window of -10 minutes recommended where feasible (but up to -30 minutes permitted if assessments are performed in different locations in hospital)**

Section of protocol affected:

Table 5 PK blood sample schedule

Previous text:

Time relative to dose	Cycle 1 Day 1	Cycle 2 Day 1	Cycle 3 Day 1
Pre-dose (±5 min)	X	X	X
1 hour (±5 min)	X		X
2 hours (±10 min)	X		X
4 hours (±10 min)	X		X
6 hours (±10 min)	X		X
8 hours (±10 min)	X		X
10 hours (±10 min)			X
12 hours (±1 hour)			X
24 hours (±1 hour)			X (D2, pre-dose)

Revised text:

Time relative to dose	Cycle 1 Day 1	Cycle 2 Day 1	Cycle 3 Day 1
Pre-dose (-10 to 0 min) ¹	X	X	X
1 hour (±5 min)	X		X
2 hours (±10 min)	X		X
4 hours (±10 min)	X		X
6 hours (±10 min)	X		X
8 hours (±10 min)	X		X
10 hours (±10 min)			X
12 hours (±1 hour)			X
24 hours (±1 hour)			X (D2, pre-dose)

1 Window of -10 minutes recommended where feasible (but up to -30 minutes permitted if assessments are performed in different locations in hospital)

Section of protocol affected:

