7.2 Dose and treatment regimens

Previous text:

AstraZeneca will supply AZD9291 as tablets for oral administration as a single daily dose of 80 mg. Patients (with the exception of patients with insulin dependent diabetes) must fast for ≥ 1 hours prior to taking a dose to ≥ 2 hour post dose. Water is permitted during this fasting period. Patients will be required to fast (water only) for at least 8 hours prior to the collection of a fasting glucose sample as per the study plan (Table 1) and Section 5.2.1.

Revised text:

AstraZeneca will supply AZD9291 as tablets for oral administration as a single daily dose of 80 mg. Patients (with the exception of patients with insulin dependent diabetes) must fast for ≥ 1 hours prior to taking a dose to ≥ 2 hour post dose. Water is permitted during this fasting

period. **All patients (including insulin dependent diabetics)** will be required to fast (water only) for at least 8 hours prior to the collection of a fasting glucose sample as per the study plan (Table 1) and Section 5.2.1.

Section of protocol affected:

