8.5 Calculation or derivation of safety variable(s)

Previous text:

Safety Assessments

For change from baseline summaries for vital signs, laboratory data, LVEF, ECGs and physical examination, the baseline value will be the latest result obtained prior to the start of investigational product.

Revised text:

Safety Assessments

For change from baseline summaries for vital signs, laboratory data, LVEF, ~~ECGs~~ and physical examination, the baseline value will be the latest result obtained prior to the start of investigational product. **For ECGs, baseline values will be taken from the screening visit, either the pre-dose time point or time-matched time points.**

Section of protocol affected:

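### The 14-day laboratory waiver can remove the fasting Day 1 glucose, and the single baseline in 8.5 then compares fasting with random values

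*Supplement*

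**What the plan says.** - **Sampling state.** Footnote 1 to Table 2 (section 5.2.1) imposes a fast of at least 8 hours before the "collection of a fasting glucose sample required on PK days". For every other day it says "Random glucose sample will be collected on non-PK days". Section 7.2, as revised by Amendment 2, extends the 8-hour fast to all patients, including those with insulin-dependent diabetes.
- **Which days are PK days.** Table 5, in its Amendment 2 form, has columns for Day 1 of Cycles 1, 2 and 3 only. Section 5.2.4 names screening separately from the PK days: "the Screening Visit and PK sampling days will require three ECGs to be performed at the following time points".
- **The waiver.** Under 5.2.1, if screening chemistry, haematology and urinalysis "have been performed within 14 days prior to starting study treatment they do not have to be repeated on Visit 2", provided the patient's condition is unchanged. Table 1 footnote h repeats the rule. Neither place excepts glucose.
- **The baseline.** For laboratory change from baseline, section 8.5 as revised by Amendment 2 says "the baseline value will be the latest result obtained prior to the start of investigational product". The same revision gives ECGs a baseline rule of their own; glucose stays under the general one.
- **Reporting.** Section 8.9.2 leaves the detail of safety summaries to the SAP, which is not among the documents shown.

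**The concern.** Change from baseline in glucose means something only if both values were taken in the same state. Two rules stand in the way. The waiver can delete the one fasting value taken before treatment, and the latest-result baseline takes whichever value came last, fasting or random.

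If random glucose tends to run higher than fasting glucose, a random baseline would hide a rise at the fasting visits, and a fasting baseline would suggest a rise at the random visits. This is a single-arm trial, so no control group would show the same pattern and expose it as a product of the schedule.

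The laboratory summary also carries some weight here. Under section 6.3.6, deterioration in a protocol-mandated laboratory value is reported as an adverse event only if it meets a seriousness criterion or leads to discontinuation, because those results are summarised in the study report. Associated signs and symptoms are reported, but a symptomless rise in glucose would show mainly in the summary.

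**Working it through.** The plan states no figure for this comparison, so there is none to reproduce. The check classifies each scheduled chemistry visit and counts mismatches.

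**Inputs.** Chemistry visits from Table 1; PK days from Table 5 (Amendment 2); sampling state from Table 2 footnote 1; baseline rule from 8.5 (Amendment 2).

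**Step 1: the two possible baselines.** If the Visit 2 chemistry is taken, the latest result before treatment is the Cycle 1 Day 1 value, specified as fasting. If it is waived, the latest result is the screening value, specified as random.

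**Step 2: post-baseline visits up to Cycle 7 Day 1.**

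| Visit | Specified state | Against fasting Day 1 baseline | Against random screening baseline |
|---|---|---|---|
| C1 D8 | random | mismatch | match |
| C1 D15 | random | mismatch | match |
| C2 D1 | fasting | match | mismatch |
| C3 D1 | fasting | match | mismatch |
| C4 D1 | random | mismatch | match |
| C5 D1 | random | mismatch | match |
| C6 D1 | random | mismatch | match |
| C7 D1 | random | mismatch | match |
| Mismatches | | 6 of 8 | 2 of 8 |

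For a waived patient, the 2 mismatches are both of the on-treatment fasting values.

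**Step 3: who is affected.** Any patient who reaches C2 D1 has at least one mismatch. With a random baseline it is C2 D1 itself; with a fasting baseline the scheduled Day 8 and Day 15 samples already mismatch. A waived patient who leaves before C2 D1 has none (0 of 1 or 0 of 2 visits).

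**Step 4: form of the distortion.** Let d be the mean of random minus fasting glucose and w the waived fraction, with d the same in waived and other patients. If the two states are pooled against the 8.5 baseline, the mean change is shifted by

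- +(1 − w)d at random visits, from the non-waived patients;
- −wd at fasting visits, from the waived patients.

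The artificial step between a random and a fasting visit is (1 − w)d + wd = d, whatever w is. The documents give neither d nor w, so no value can be put in.

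**Step 5: is the Day 1 draw already planned?** Table 3 allows 15 mL of safety blood per visit and 45 mL in Cycle 1. 45 / 15 = 3 draws, that is Days 1, 8 and 15. The mandatory total also includes it: 90 + 32 + 70 = 192 mL, as section 5.2.2 states.

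**The case against.** The strongest reply is that nothing shown says fasting and random glucose will be pooled. Section 8.5 only picks the baseline value, and the layout of safety tables is left to the SAP, which could treat the two as separate parameters. For a patient not waived this largely answers the point: a random screening value and a fasting Day 1 value both exist, and the visit schedule tells them apart. It does not help a waived patient, whose fasting value before treatment was never taken.

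A second reply is that footnote 1 makes the Day 1 fasting sample a requirement and Table 3 budgets the draw, so the specific rule might be read as overriding the general waiver. That reading is possible. But the waiver covers the whole chemistry panel without exception in two places, and a site following it would be within the protocol. The conflict has to be resolved in the text.

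Third, random on treatment does not mean freshly fed. Chemistry is drawn before the dose, and section 7.2 has patients other than those with insulin-dependent diabetes fast for at least an hour before dosing. Some random samples will be fasting by chance. This stands: the mismatch is in the specified condition, and its effect may be small.

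A reader might infer that every patient is affected, or attach a bias in mmol/L to the Cycle 2 and 3 means. The documents support neither. Waived patients who leave before Cycle 2 Day 1 have no mismatch, and any figure would rest on an assumed gap between random and fasting glucose and an assumed use of the waiver.

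**Conclusion.** The point holds, as a minor one. Footnote 1 and the 14-day waiver conflict for Cycle 1 Day 1 glucose. Where the waiver is used, the fasting values at Cycles 2 and 3 have no fasting baseline, and this cannot be repaired at analysis. Where it is not used, the 8.5 baseline sets a fasting value against random values at 6 of the 8 scheduled visits to Cycle 7 Day 1, unless the SAP separates the two states.

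A mismatch arises for any patient who reaches Cycle 2 Day 1, or who has a fasting Day 1 baseline and a later non-PK sample. The counts assume that samples are taken in the state the protocol specifies. The reach is limited to one descriptively summarised laboratory variable; the response rate and the other efficacy analyses are untouched.

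**What to change.** 1. In 5.2.1 and Table 1 footnote h, reconcile the waiver with footnote 1 by exempting glucose, so that the fasting sample is always drawn before the dose on Cycle 1 Day 1.
2. In 8.5 or the SAP, summarise the two states separately: change in fasting glucose from the Day 1 fasting value, and change in random glucose from the screening random value.

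The cost is one local glucose assay for each waived patient and one analysis sentence. The PK and ctDNA draws on that day do not supply the result, because chemistry is run at local laboratories, but Table 3 already counts a Day 1 safety draw. The specified fasting state follows from the visit schedule, so a field recording it on the case report form is optional.
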